6.1. Investigational Medicinal Product Administered

Each subject will be randomized to receive treatment with the IMP (C21 or placebo). The IMP will be administered as a capsule for oral administration. Each subject will receive 4 capsules per day, divided in 2 doses given twice a day.

IMP will be administered in fasting conditions (see Section 5.3). C21 is an AT2R agonist. The drug substance is 3-[4-(1H-imidazol-1-ylmethyl)phenyl]-5-(2-methylpropyl)thiophene-2-[(N-butyloxylcarbamate)-sulphonamide] sodium salt supplied as a free form equivalent (eq.) 50 mg C21 oral capsule.

Table 1. Investigational Medicinal Product Administered

IMP Name	Active / C21	Placebo
Dose Formulation	Capsule	Capsule
Unit Dose Strength(s)	52.3 mg pr capsule	Placebo
Dosage Level(s)	2 capsules, b.i.d.	2 capsules, b.i.d.
Excipients	Mannitol, Anhydrous colloidal silica, Magnesium stearate	Mannitol, Anhydrous colloidal silica, Magnesium stearate
Capsule	Vcaps® plus	Vcaps® plus
Route of Administration	Oral	Oral
Dosage description	Subjects will receive 100 mg C21 b.i.d. on Day 1 to Day 14.	Subjects will receive Placebo b.i.d. on Day 1 to Day 14.
Sourcing	Provided centrally by the sponsor	Provided centrally by the sponsor
Packaging and Labeling	IMP will be provided in a container. Each container will be labeled as required per country requirement.	IMP will be provided in a container. Each container will be labeled as required per country requirement.

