6.4. Investigational Medicinal Product Compliance

When subjects are randomized at the site, they will receive the IMP doses directly from the investigator or designee, under medical supervision. The date and time of each dose administered in the clinic will be recorded in the source documents. The IMP container number and trial

subject identification will be confirmed at the time of dosing by a member of the trial site staff other than the person dispensing the IMP.

During the hospitalization, the investigator or designee should investigate and document if the fasting criteria for the IMP (see Section 5.3) has been fulfilled.

If a subject is discharged from the hospital prior to Day 15 and self-administer the remaining IMP at home, IMP compliance and compliance with fasting criteria will be assessed at Visit 16 (Day 15) and documented in the source documents and the eCRF relevant form. Deviation(s) from the prescribed dosage regimen and fasting criteria should be recorded.

A record of the quantity of IMP dispensed to and administered by each subject must be maintained and reconciled with IMP and compliance records. Intervention start and stop dates, including dates for intervention delays and/or dose reductions will also be recorded.

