7.1.1. Temporary Discontinuation

There are no specific criteria for temporary discontinuation of IMP treatment. If temporary discontinuation of IMP is required according to investigator's judgement, the date and reason for a temporary discontinuation should be reported in the eCRF. If the subject is still within the treatment period of the trial when a temporary discontinuation is no longer required, IMP treatment can be restarted.

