	Screening	IMP Treatment Period				In-patient Stay ¹⁾	Follow-up Period ²⁾			Unscheduled ³⁾
Visit	V1	V2	V3-15 ¹⁾ ⁴⁾	V16 ⁴⁾	EWD ⁵⁾	V17-29	V30	V31	V32	UV
Day (Visit window)	Up to 48h prior to V2	Day 1	Days 2-14	Day 15 (+1 day)		Days 16-28	Day 22 (±1 days)	Day 29 (±1 days)	Day 60 (±3 days)	
Eligibility/General										
Informed consent	x									
Eligibility criteria	x	x ⁶⁾								
Demographics	x									
Medical history	x									
IMP and Concomitant Therapy										
Randomization		x								
IMP administration ⁷⁾		x	x							(x)
Check of fasting criteria		x	x							(x)
IMP accountability			x ⁸⁾	x	x					
Previous and concomitant therapy	x	x	x	x	x	x	x	x		(x)
Trial Assessments and Procedures										
8-point ordinal scale	x	x	x	x	x	x	x	x	x	(x)
Supplemental O ₂	x	x	x	x	x	x	x	x	x	(x)
Oxygen saturation	x	x	x	x	x	x				(x)
Hospitalization	x	x	x	x	x	x	x	x	x	(x)
Physical examination	x			x	x					(x)
Body weight and height	x									
Vital signs	x	x	x	x	x	x				(x)
12-lead ECG ⁹⁾	x									(x)
Adverse events	x	x	x	x	x	x	x	x	x ¹⁰⁾	x
Biochemistry ¹¹⁾	x	x ¹²⁾	Days 3, 5, 8, 11 (all ± 1 day)	x	x					(x)
Haematology ¹¹⁾	x	x ¹²⁾	Days 3, 5, 8, 11 (all ± 1 day)	x	x					(x)
Urinanalysis ¹¹⁾	x	x ¹²⁾		x	x					(x)
Pregnancy testing ¹³⁾	x			x	x					(x)
Oropharyngeal swab		x								
Pharmacokinetics ¹⁴⁾		x								
Blood sample for future exploratory analysis		x ¹²⁾		x	x					

1. Daily visits until discharge. Visits will be re-initiated in case of a COVID-19 related hospital re-admission.
2. Follow-up visits by phone or video.
3. Assessments marked with () will be performed per investigator judgment at e.g., COVID-19 related hospital re-admission after Day 29.
4. Days 8 and 15 visits must be performed for all subjects. If a subject is discharged before Day 8, the Day 8 visit will be done by phone or video. Site assessments e.g., oxygen saturation, vital signs and blood sampling will not be performed.
5. An early withdrawal (EWD) visit should be performed for subjects withdrawn from the trial prior to Day 15 (Visit 16).
6. Re-evaluation of eligibility including evaluation of electrocardiogram (ECG) and laboratory results from screening.
7. IMP is administered b.i.d. from Days 1 to 14.
8. IMP accountability will be performed at hospital discharge.
9. A historical 12-lead ECG is acceptable. The ECG should be ≤2 days old at the time of screening (Visit 1).
10. SAEs only.

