12.3 Treatments

12.3.1 Extent of Trial Drug Exposure

For the IMP, summary statistics will be provided for SS for duration of exposure, total number of dose administrated and total cumulative dose in the treatment period. The number and percentage of subjects who experience at least one overdose on any day during the treatment period will be provided. Any dose of C21 exceeding a total daily dose of 200 mg (i.e., 4 capsules of IMP) is considered an overdose.

The total cumulative dose will be calculated as:

Cumulative dose (mg) = 50x (Number of Capsules dispensed [56] – Capsules returned)

The total number of doses administered will be the difference between the number of capsules dispensed [56] and number of capsules returned. If returned amount is missing and the subject is indicated to have completed treatment, they will be treated as taking all capsules. If the subject discontinues treatment and

returned amount is missing, they will be treated as taking capsules as planned up to the day of discontinuation derived as:

$$\text{Cumulative dose (mg)} = 50 * (4 * (\text{duration of exposure}))$$

where duration of exposure for this calculation will be set to a minimum of duration of exposure and 14 days.

If first dose for subject that discontinues treatment and has no returned amount is in the evening (p.m.) the calculation will be as follows:

$$\text{Cumulative dose (mg)} = 50 * (2 + 4 * (\text{duration of treatment} - 1))$$

For these subjects with first dose in the p.m., if duration of exposure is >14 indicating the subject took the full treatment course, the cumulative dose will be assumed to be 56.

The duration of exposure will be derived as:

$$\text{Duration} = (\text{Last dose of IMP} - \text{First dose of IMP}) + 1$$

Duration of exposure will be summarized overall, by subjects whose first dose was in the morning and by subjects whose first dose was an evening dose. Duration of exposure will also be summarized by duration categories, the number of subjects exposed for 1-6 days, 7-13 days and 14+ days.

Overall compliance will be calculated as follows:

$$\text{Treatment Compliance (\%)} = 100 * \frac{\text{Total Number of Doses administered}}{\text{Expected Number of Capsules}}$$

For subjects who completed treatment, expected number of capsules will be 56. For subjects who discontinue treatment:

$$\text{Expected Number of Capsules} = 4 * \text{Duration of exposure}$$

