Compliance will be summarized using the following categories: <80%, 80-90%, >90%.

The percentage of doses taken in hospital will be presented and derived as follows:

$$\% \text{ of Doses taken} = 100 * \frac{56 - \text{Number of Capsules dispensed on discharge}}{\text{Cumulative dose (total capsules taken)}}$$

For subjects who do not discharge during the treatment period or who discontinue the study prior to discharge from hospital during the treatment period, the % doses taken will be 100%.

The number of doses missed and reason dose missed will be summarized for subjects (this information will only be collected during the hospitalized period). Trial drug exposure will be listed. Drug accountability will also be listed.

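### When the returned capsule count is missing, SAP 12.3.1 credits every planned capsule and ignores missed doses recorded in hospital, so exposure and compliance are overstated for the subjects affected

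*SAP*

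**What the plan says.** SAP 12.3.1 gives the main formula as "Cumulative dose (mg) = 50x (Number of Capsules dispensed [56] – Capsules returned" (bracket closed). Compliance is capsules taken over capsules expected. The expected number is 56 for completers and 4 x duration of exposure for discontinuers, and results are reported as below 80%, 80-90% and above 90%.

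Two fallback rules apply when the returned count is missing:
- Completers: "If returned amount is missing and the subject is indicated to have completed treatment, they will be treated as taking all capsules".
- Discontinuers: "they will be treated as taking capsules as planned up to the day of discontinuation". This is 4 capsules per day of exposure, or 2 + 4 x (duration - 1) if the first dose was in the evening.

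The same section continues: "The number of doses missed and reason dose missed will be summarized for subjects (this information will only be collected during the hospitalized period" (bracket closed). Protocol 7.1.1 adds that, for an interruption, "the date and reason for a temporary discontinuation should be reported in the eCRF". Protocol 6.4 has compliance of discharged subjects assessed at Visit 16 and entered in the eCRF: "Deviation(s) from the prescribed dosage regimen and fasting criteria should be recorded". Neither document tells the analyst to take any of these records into account when the returned count is missing.

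**The concern.** A fallback for a missing value should use whatever else is known about the subject. Here it fixes the answer. Compliance is 100% for every completer without a returned count, and 100% for every morning-start discontinuer with up to 14 days of exposure, whatever the missed-dose records show. An omitted dose can only have lowered the true intake, so ignoring it always overstates the capsules taken.

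At stake is the internal consistency of the exposure section of the report. One table could show a subject with six missed doses while the compliance table counts that subject as fully compliant. Cumulative dose would be overstated for the same subject.

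**Working it through.** **Inputs**
- Dose schedule: "Each subject will receive 4 capsules per day, divided in 2 doses given twice a day" (Protocol 6.1), so one dose is 2 capsules.
- Duration: "IMP is administered b.i.d. from Days 1 to 14" (schedule of activities in SAP 8.0), so 14 days.
- 50 mg per capsule, 56 capsules dispensed, and the denominators and categories above (SAP 12.3.1).
- Numbers of missed doses (k) and days of exposure (d) below are chosen for illustration.

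**The plan's own figure.** 14 days x 4 capsules = 56 capsules, and 56 x 50 mg = 2800 mg. Both reproduce.

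**Completer, count missing.** The SAP credits 56/56 = 100% and 2800 mg for any k. With recorded misses subtracted, capsules taken = 56 - 2k and compliance = 100 x (56 - 2k)/56. Each ignored dose is worth 2 x 50 = 100 mg and 100 x 2/56 = 3.6 points.

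| Missed doses | Capsules | Dose (mg) | Compliance | Category | SAP reports |
|---|---|---|---|---|---|
| 0 | 56 | 2800 | 100% | >90% | >90% |
| 1 | 54 | 2700 | 96.4% | >90% | >90% |
| 2 | 52 | 2600 | 92.9% | >90% | >90% |
| 3 | 50 | 2500 | 89.3% | 80-90% | >90% |
| 6 | 44 | 2200 | 78.6% | <80% | >90% |

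Six doses correspond to a 3-day interruption.

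**Discontinuer, morning first dose, d up to 14.** The SAP gives 4d/4d = 100%. With subtraction it is (4d - 2k)/4d, so each dose is worth 2/(4d). At d = 7 that is 2/28 = 7.1 points, and three missed doses give 22/28 = 78.6% against a reported 100%.

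**Discontinuer, evening first dose.** The SAP gives (4d - 2)/4d. At d = 7 that is 26/28 = 92.9%. Three missed doses give 20/28 = 71.4% on the SAP denominator, or 20/26 = 76.9% of the capsules actually due. With no missed dose the SAP value is too low: at d = 5 it is 18/20 = 90%, although all 18 capsules due were taken.

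**Effect on the mean.** The documents do not say how many subjects would be affected. Assuming affected completers make up 1% to 10% of subjects, with 1 to 3 missed doses each, mean compliance shifts by between 0.01 x 3.57 = 0.04 and 0.10 x 3 x 3.57 = 1.1 points.

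**The case against.** The strongest defence is that this is a disclosed simplification on a descriptive table. Protocol 6.2 requires all IMP to be returned at Visit 16 or at early withdrawal, so the fallback covers exceptions. The rule is the same in both arms. Missed doses are tabulated separately, and exposure and accountability are listed, so a reader could trace any discrepancy. This stands as an argument about importance. It does not justify overriding a recorded value.

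The defence also limits the remedy, and this stands. Missed-dose counts are collected only in hospital. Protocol 7.1.1 asks for a date and reason for an interruption, not a number of doses. Nothing shows that the Visit 16 form captures a number of missed doses. Subtracting from several sources without a rule could count one withheld dose twice.

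The SAP change history remarks that individual dose administration is not recorded. That remark concerns how actual treatment is assigned (SAP 10.4). It does not displace the current statement in SAP 12.3.1 that missed doses are collected in hospital.

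A reader might infer three stronger points that the documents do not support:
- **The error falls mainly on discharged subjects who do not bring the container back.** This is plausible, but neither document says where counts go missing.
- **Compliance categories drive interpretation or per-protocol membership.** SAP 12.5.2.3 mentions 80% compliance, but only to explain a cut-off at Day 11 for stopping by subject decision. SAP 9.5.3 builds the set from deviations, that cut-off, untreated status and blinded review. The primary analysis is by ITT under a treatment policy.
- **Every fallback value is too high.** The evening-start discontinuer with no missed dose is a counterexample.

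**Conclusion.** The point holds as a minor defect. The fallback is a stated rule that gives a wrong value against hospital missed-dose data the SAP says are collected. For an affected completer, three ignored doses move the subject up one compliance category and six move the subject up two. For discontinuers the error per dose is larger because the denominator is smaller.

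The effect requires both a missing returned count and at least one recorded missed dose, and the frequency of that combination is unknown. It reaches number of doses, cumulative dose and compliance only. The missing-count rule does not alter duration of exposure, the per-protocol set or any efficacy analysis, and no bias between arms is shown.

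**What to change.** In SAP 12.3.1, for a missing returned count:
- Set capsules taken to the planned capsules up to end of treatment (keeping the evening-start adjustment) minus 2 for each dose recorded as missed in hospital.
- Count each dose once, even if it also appears under a temporary discontinuation.
- Subtract home-period doses only where the eCRF gives a count or dates.
- Flag these subjects and report how many rely on an assumed home dose.

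The cost is a few sentences in the SAP and minor programming. The hospital part needs no new data. The home part depends on what the CRF records, which the two documents do not show. The evening-start denominator is a separate correction that could be made in the same edit.

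### SAP 12.3.1 uses cumulative dose in two units, and its compliance denominator for discontinued subjects ignores partial first and last dosing days

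*SAP*

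**What the plan says.** The regimen is in Protocol 6.1: "Each subject will receive 4 capsules per day, divided in 2 doses given twice a day", and "Subjects will receive 100 mg C21 b.i.d. on Day 1 to Day 14".

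SAP 12.3.1 defines cumulative dose in mg: "Cumulative dose (mg) = 50x (Number of Capsules dispensed [56] – Capsules returned"). When a subject discontinues and the returned amount is missing, "they will be treated as taking capsules as planned up to the day of discontinuation". For a morning starter that is 50 x 4 x duration, with duration capped at 14 days. For an evening starter it is 50 x (2 + 4 x (duration - 1)). If an evening starter in this group has a duration above 14 days, "the cumulative dose will be assumed to be 56", with no unit.

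Further down the same section, the percentage of doses taken in hospital has cumulative dose as its denominator, glossed in brackets as total capsules taken.

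Compliance is 100 x capsules taken / expected capsules. Expected capsules are 56 for completers. "For subjects who discontinue treatment", they are 4 x duration of exposure, where duration is last dose date minus first dose date plus 1. Neither the time of the first dose nor the time of the last dose enters. "Compliance will be summarized using the following categories": <80%, 80-90% and >90%.

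**The concern.** There are two separate faults.

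**Unit.** One term carries two units within one section. Three formulas give cumulative dose in mg, one rule assigns it a bare capsule count, and one ratio divides by it as a capsule count. Programmed literally, a subject presumed to have taken the whole course would enter the mg summary with 56, little more than one 50 mg capsule.

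**Denominator.** The section gives two planned counts for the same person. An evening starter who stops is credited with 4D - 2 capsules as the planned number over D days, then judged against 4D. Someone who missed nothing cannot reach 100%, and the shortfall is largest for the earliest stoppers. A reader of the compliance table would take some of them to be non-adherent.

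**Working it through.** **Inputs.** 4 capsules per day for 14 days (Protocol 6.1). 50 mg per capsule, 56 capsules dispensed, D = last dose date - first dose date + 1, and the compliance classes (all SAP 12.3.1).

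**1. The figure 56.**
- As capsules: 4 x 14 = 56. The figure reproduces.
- As mg: 50 x 56 = 2,800, and 100 mg x 2 x 14 = 2,800. The figure does not reproduce; read as mg it is too low by a factor of 2,800 / 56 = 50.
- Purpose of the rule: at D = 15 the evening-start formula gives 2 + 4 x 14 = 58 capsules (2,900 mg), more than were dispensed. So 56 is evidently a cap in capsules.

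**2. Compliance of a discontinued subject who took every dose due while on treatment.** The SAP divides by 4D in every case.
- Evening start, evening last dose: 4D - 2 capsules taken, so compliance = 100 x (1 - 1/(2D)). This numerator is the SAP's own planned count.
- Evening start, morning last dose (D of 2 or more): 4D - 4 taken, so 100 x (1 - 1/D).
- Morning start, morning last dose: 4D - 2 taken, so 100 x (1 - 1/(2D)).

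| D | p.m. start, p.m. last: capsules, % | p.m. start, a.m. last: capsules, % | a.m. start, a.m. last: capsules, % |
|---|---|---|---|
| 1 | 2, 50.0 | not possible | 2, 50.0 |
| 2 | 6, 75.0 | 4, 50.0 | 6, 75.0 |
| 3 | 10, 83.3 | 8, 66.7 | 10, 83.3 |
| 4 | 14, 87.5 | 12, 75.0 | 14, 87.5 |
| 5 | 18, 90.0 | 16, 80.0 | 18, 90.0 |
| 6 | 22, 91.7 | 20, 83.3 | 22, 91.7 |
| 10 | 38, 95.0 | 36, 90.0 | 38, 95.0 |
| 11 | 42, 95.5 | 40, 90.9 | 42, 95.5 |

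All of these subjects belong in >90%. With one partial day, the class is <80% for D = 1 or 2, 80-90% for D = 3 to 5, and correct from D = 6. With both days partial, it is <80% for D = 2 to 4, 80-90% for D = 5 to 10, and correct from D = 11.

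**3. Would adjusting only for the evening start be enough?** No. With expected = 2 + 4 x (D - 1), an adherent evening starter whose last dose is the next morning took 4 of 6 capsules, 66.7%, and is still classed <80%. At D = 15 the expected count is 58, so a full course of 56 scores 56/58 = 96.6%.

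**4. Does the ratio feed any analysis set?** SAP 9.5.3 and 12.5.2.3 exclude subjects from the per-protocol set by the day and reason of stopping, plus blinded review. SAP 12.5.2.3 does equate stopping up to Day 11 with less than 80% compliance, but that works only against the full course: 4 x 11 = 44, and 44/56 = 78.6%. It is not the 12.3.1 ratio, which divides by days actually on treatment.

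**The case against.** The best defence on the unit is that the intent is plain. The same section labels 56 as capsules dispensed, the sentence refers to a full course, and the in-hospital ratio glosses cumulative dose as capsules. On that reading a label is missing and no dose is wrong. This largely stands: a reader might infer that the reported dose will be understated 50-fold, but that happens only if 56 is coded as mg. It also needs an evening start, a recorded discontinuation, no returned count and a duration above 14 days; completers with a missing count are handled by another rule. What remains is that the specification uses one term in two units and leaves the programmer to guess.

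On compliance, a reader might infer that fully adherent evening starters who stop early are generally classed <80%. The SAP's formulas do not support that: the class depends on how soon dosing stopped and on the time of the last dose, and most later stoppers fall in the right class. Nor is the fault confined to evening starters.

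It can also be said that the tables are descriptive, that duration is summarized separately for morning and evening first doses, and that exposure and accountability are listed, so the half-day effect can be traced. All true. It limits the consequence but does not make the printed compliance class correct.

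**Conclusion.** Both faults are real and minor. The rule that assigns 56 should read 2,800 mg if the variable is in mg, and the term should not also denote capsules. The 4 x duration denominator understates compliance for every adherent discontinued subject with a partial first or last day. It changes the class only for early stoppers: up to 5 days with one partial day, up to 10 days with both.

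The effect stays within descriptive exposure and compliance tables. A reader might infer from the mention of 80% compliance in SAP 12.5.2.3 that per-protocol membership is affected; it is not, because membership rests on day and reason of stopping. No efficacy test changes.

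Assumptions: the subject took every dose due up to stopping, and dosing is 2 capsules per occasion as planned. The documents give no count of affected subjects. That they are few is a judgement from how narrow the conditions are.

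**What to change.** In SAP 12.3.1:

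1. Replace the bare 56 with 2,800 mg (56 capsules).
2. In the in-hospital percentage, name the denominator total capsules taken and drop the term cumulative dose.
3. For discontinued subjects, set expected capsules = min(56, 4 x duration - 2 if the first dose was in the evening - 2 if the last dose was in the morning because treatment stopped before the evening dose). Adherent subjects then score 100%: for example 6/6 and 4/4 for an evening starter at D = 2 with an evening or morning last dose, and 56/56 for a full course at D = 15.
4. Say what to assume when the time of the last dose is unknown. Under SAP 10.3 the last dose of a subject discharged before the end of treatment is a date from the End of Treatment page, so the time of day may not be available.

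The cost is a few lines of SAP text and matching code. Trial conduct and type I error control are untouched, and no new data are needed if item 4 is settled by a stated convention.

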9.5.3 Per Protocol Analysis Set

The per protocol analysis set (PP) comprises all subjects in the ITT without important protocol deviations deemed to have an impact on efficacy endpoints. In addition, subjects who prematurely discontinued IMP prior to Day 11 during the treatment period due to "Withdrawal by Subject" or similar will be excluded. Subjects who were randomized and not treated will also be excluded from the PP population.

Prior to database lock and unblinding of the trial, a blinded data review of the important protocol deviations will be performed to identify the important deviations impacting on the efficacy endpoints. Additionally a review of all subjects who discontinue treatment will be performed to assess if they should be excluded from the PP. Subjects excluded together with the reason for exclusion will be documented in a blinded manner prior to database lock. Subjects will be included in the analyses according to the intervention they were randomized to.

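### SAP 12.3.1: expected capsules for discontinuers do not match the SAP's own count of capsules taken, so subjects it treats as fully adherent can score below 100%

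*SAP*

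**What the plan says.** Protocol 6.1 gives 4 capsules a day in two doses, for 14 days. In SAP 12.3.1 the number administered is the 56 capsules dispensed minus those returned. When the return count is missing, the rules are:

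- Completers: "If returned amount is missing and the subject is indicated to have completed treatment, they will be treated as taking all capsules".
- Discontinuers in general: "they will be treated as taking capsules as planned up to the day of discontinuation". The dose is 50 mg × 4 × duration of exposure, with duration limited to 14 days for that calculation.
- Evening starters: "If first dose for subject that discontinues treatment and has no returned amount is in the evening (p.m.) the calculation will be as follows", namely 50 mg × (2 + 4 × (duration of treatment − 1)). Beyond 14 days, "if duration of exposure is >14 indicating the subject took the full treatment course, the cumulative dose will be assumed to be 56".

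The compliance denominator is set separately: "For subjects who completed treatment, expected number of capsules will be 56. For subjects who discontinue treatment" it is 4 × duration of exposure. Duration is last-dose date minus first-dose date plus 1. Results are tabulated as below 80%, 80 to 90%, and above 90%.

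**The concern.** The numerator for an evening starter leaves out the two Day 1 morning capsules because they were never due. The denominator puts them back as expected. A subject whom the SAP assumes to have missed nothing is then reported as less than fully compliant. A morning starter under the same missing-return rule scores 4d/4d = 100% up to d = 14, so only the clock time of the first dose separates the two.

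The lack of a cap produces a second mismatch. Past 14 days the capsules credited stop at 56, but the capsules expected keep rising. At stake is the accuracy of a descriptive table: some discontinuers would appear in a low-compliance category although the plan treats them as having taken everything planned.

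**Working it through.** **Inputs.** 4 capsules a day as 2 + 2 (Protocol 6.1). Credited capsules, expected capsules, duration d and categories are from SAP 12.3.1. Two readings are needed. First, duration of treatment in the evening formula means the defined duration of exposure. Second, capsules taken equal the derived cumulative dose divided by 50 mg. The second reading is natural because 56 minus returned cannot be computed when the return count is missing.

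**The plan's own figure.** Full course: 4 × 14 = 56, as stated. An evening start also reaches 56, as 2 (Day 1 evening) + 4 × 13 + 2 (Day 15 morning).

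**No return count, evening start.** Compliance = (2 + 4(d − 1)) / (4d) = 1 − 1/(2d) for d = 1 to 14. At d = 15 the SAP credits 56.

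| d | Credited | Expected (4d) | Compliance | Category reported |
|---|---|---|---|---|
| 1 | 2 | 4 | 50.0% | below 80% |
| 2 | 6 | 8 | 75.0% | below 80% |
| 3 | 10 | 12 | 83.3% | 80 to 90% |
| 4 | 14 | 16 | 87.5% | 80 to 90% |
| 5 | 18 | 20 | 90.0% | 80 to 90% |
| 6 | 22 | 24 | 91.7% | above 90% |
| 14 | 54 | 56 | 96.4% | above 90% |
| 15 | 56 | 60 | 93.3% | above 90% |

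The value implied by taking capsules as planned is 100% in every row, so the category is wrong at d = 1 to 5.

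**No return count, morning start.** 4d/4d = 100% for d = 1 to 14. At d = 15 the dose calculation is capped at 4 × 14 = 56 but the denominator is 4 × 15 = 60, giving 93.3%.

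**Return count present, every due dose taken.**

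- Evening first and evening last dose: 4d − 2 capsules against 4d, the same percentages as in the table for d = 1 to 14.
- Morning first and morning last dose: also 4d − 2 against 4d, so again 50.0% to 90.0% at d = 1 to 5.
- Evening first and morning last dose: 4d − 4 against 4d. This gives 50.0% at d = 2, 75.0% at d = 4, 80.0% at d = 5, 90.0% at d = 10 and 90.9% at d = 11, so the category is wrong at d = 2 to 10.
- Morning first and evening last dose: 4d against 4d, 100%.

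**Completers.** Denominator 56. They score 100% if they took 56 capsules or have no return count, so they are not affected.

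**Proposed denominator, no return count.** Evening start: 2, 6, 10, 14, 18, 22 for d = 1 to 6, then 54 at d = 14 and min(56, 58) = 56 at d = 15. Morning start: 4d up to 56, and min(56, 60) = 56 at d = 15. The ratio is 100% at every d from 1 to 15 in both groups.

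**The case against.** The case for leaving the rule alone is mainly about reach. The clearest failure needs an evening start, discontinuation and a missing return count, and the category changes only if the subject stops within five days. Doses in hospital are supervised and timed (Protocol 6.4), and unused product is to be returned at Day 15 or at early withdrawal (Protocol 6.2), so missing counts in early discontinuers should be uncommon. The SAP also lists exposure and drug accountability and summarizes missed in-hospital doses, so true dosing can be recovered. The evening formula is written for cumulative dose in mg, and its link to the compliance numerator has to be inferred. All of this stands, and it limits how much the point matters.

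The rule could also be defended as a deliberately coarse or conservative denominator. That does not stand. The SAP says these capsules are taken as planned, makes an explicit evening adjustment in the numerator, and gives a morning starter in the same position 100%.

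A reader might infer that the error belongs to evening starters alone and that the morning rule is sound. The documents do not support that. The whole-day, uncapped denominator also gives 93.3% to a morning starter at d = 15 with no return count. It understates a fully adherent morning starter who has a return count and whose last dose was in the morning.

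**Conclusion.** The inconsistency is real and minor. For discontinuers without a return count, evening starters are understated at every d from 1 to 15 and misclassified at d = 1 to 5, while morning starters are affected only beyond Day 14. Fully adherent discontinuers with a return count are understated when dosing began or ended on a part-day. The conclusion rests on the two readings stated in the working. The documents give no number of evening starters, early discontinuers or missing return counts, so the number of subjects affected cannot be estimated.

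A reader might infer that the per-protocol set is affected, because SAP 12.5.2.3 equates stopping up to Day 11 with less than 80% compliance. That is a share of the full course: 11 days of dosing is 44/56 = 78.6%. The ratio in 12.3.1 instead divides a discontinuer's capsules by those expected up to the stopping day. SAP 9.5.3 excludes "subjects who prematurely discontinued IMP prior to Day 11 during the treatment period due to" withdrawal by the subject or similar, along with relevant important deviations and untreated subjects. It does not use the 12.3.1 percentage. The compliance rule is the same in both arms. No efficacy or per-protocol analysis changes; the correction is worth making but not essential.

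**What to change.** In SAP 12.3.1, for subjects who discontinue treatment, replace the single denominator with:

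- morning first dose: Expected Number of Capsules = min(56, 4 × duration of exposure);
- evening first dose: Expected Number of Capsules = min(56, 2 + 4 × (duration of exposure − 1)).

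Keep 56 for completers. Applying the evening formula to them would give 56/54 = 103.7% for an evening-start completer with no return count who stops on Day 14. State in the text that duration of treatment means duration of exposure, and that capsules taken equal cumulative dose divided by 50 when the return count is missing.

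This gives 100% to every discontinuer treated as taking capsules as planned. Subjects with a return count and a morning last dose keep a two-capsule shortfall wherever the cap does not apply. For example, an evening starter at d = 4 scores 12/14 = 85.7%, and a morning starter at d = 4 scores 14/16 = 87.5%. Where the time of the last dose is recorded, subtract 2 from the uncapped count for these subjects. Do not subtract it when the return count is missing, because the numerator then already credits the whole last day.

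The cost is one line per first-dose group in the derivation. The main change needs no new data, since exposure is already to be summarized "by subjects whose first dose was in the morning and by subjects whose first dose was an evening dose". The optional subtraction depends on last-dose time, which Protocol 6.4 requires in source documents for doses given in the clinic.
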